THE KEY INGREDIENTS OF SUPPORTING CONFLICT-AFFECTED CAREGIVERS: A RANDOMIZED CONTROLLED TRIAL WITH MEDIATION ANALYSIS

Analysis Plan, Version 1.0

September 21, 2025

SECTION 1. ADMINISTRATIVE INFORMATION

1. Title and registration

The key ingredients of supporting conflict-affected caregivers: A randomized controlled trial with mediation analysis. This trial was registered on ISRCTN on January 27, 2025: ISRCTN89294864.

2. SAP Version: 1.0, September 21, 2025

3. Protocol version: 1.0, August 13, 2024

4. SAP revisions

None

5. Roles and responsibility

Statistician: [name]

Investigators: [name] [name], [name], [name], [name], [name], [name],

6. Signatures of person writing the SAP, senior statistician responsible, and chief investigator/clinical lead

Reviewed by all listed authors and signed by the following.

Name	Signature	Date
[name]		21/09/2025
[name]		21/09/2025
[name]		21/09/2025
[name]		17/9/2025
[name]		21/09/2025
[name]	[name]	16/09/2025
[name]		21/09/2025

SECTION 2. INTRODUCTION

This statistical analysis plan describes procedures for analyzing data from a randomized waitlist-controlled trial of the BeThere intervention on parenting in South Sudan. Relevant study design details are provided below followed by a detailed description of the statistical analysis approach. This analysis plan only covers the quantitative data analyses and excludes the qualitative analysis approach. Analyst and PI will remain masked to study condition until primary analyses have been completed.

The analyses described below will inform the development of two scientific manuscripts: 1) Effectiveness of the BeThere intervention on primary and secondary outcomes; and 2) Mediators of the effects of the BeThere intervention on child wellbeing and caregiver outcomes.

7. Background and rationale

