Parenting interventions in conflict-affected settings have often assumed that poor parenting stems mainly from a lack of knowledge or skills. However, research shows that caregiver stress and mental health challenges—driven by war exposure and daily stressors—play a central role in sub-optimal parenting. The family stress model highlights how caregiver wellbeing mediates the impact of conflict on parenting, with negative consequences for children’s psychosocial health. Studies further show that caregivers themselves are frequently perpetrators of abuse in emergencies, and that caregiver mental health is directly linked to child mental health outcomes among conflict-affected and displaced populations.

To address these interconnected factors, War Child developed *BeThere*, a nine-session preventive group intervention for caregivers of children aged 3–14 affected by armed conflict and forced migration. Grounded in the family stress model, the program combines parenting support with a strong focus on caregiver mental health. The first four sessions emphasize caregiver mental health and stress management, followed by sessions on positive parenting in adversity, with a final review session. Through this dual focus—building evidence-based parenting skills and strengthening caregiver mental health—*BeThere* seeks to improve both parenting practices and child wellbeing.

8. Objectives

The overall objective of this study is to evaluate the effectiveness of BeThere for improving parenting behaviors and child wellbeing in Bor County, South Sudan. The research objectives are as follows:

Primary Objectives

1. To evaluate the effectiveness of the BeThere intervention in improving parenting among participating caregivers in a fully-powered trial in South Sudan
2. To evaluate the effects of the BeThere intervention on participating caregivers’ children using child-reported outcomes among a subsample of children aged 7-14.
3. To estimate the indirect effect of the BeThere intervention via caregiver wellbeing, caregiver distress, caregiver stress, and parenting on child wellbeing.

Secondary Objective

4. To assess the effect of group cohesion among beneficiaries in the BeThere intervention group on caregiver wellbeing and distress

SECTION 3: STUDY METHODS

9. Trial design

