14. Timing of final analysis

All analyses will be conducted after completion of data collection for the trial. The statistician and PI will be masked to study condition during data collection, cleaning, and the primary effectiveness analyses. Secondary analyses examining mediators that relate to intervention group characteristics (e.g., BeThere Mechanism of Action, Group Cohesion) or require analysis of intervention midline assessment data will be conducted after effectiveness analyses are finalized to preserve masking.

15. Timing of outcome assessments

Data used for this study will be collected by research assistants at baseline, midline (BeThere session 5), endline (within 2-3 weeks following session 9 or approximately 10-12 weeks post-enrollment), and follow-up (12 weeks after completion of the final session or approximately 22 weeks post-enrollment). The midline assessment was only administered to the experimental (i.e., BeThere) group and not to the waitlist control group.

SECTION 4: STATISTICAL PRINCIPLES

16. Level of statistical significance

A significance level of $\alpha=0.05$ will be applied.

17. Adjustments for multiplicity

We do not plan to adjust for multiple testing.

18. Confidence intervals

Results will be presented as coefficients and 95% CIs.

19. Adherence and protocol deviations

Participant adherence to the intervention will be measured using intervention session attendance records. Completion of the intervention will be defined as having attended seven or more sessions. We will report the mean (SD) and median (IQR) number of sessions attended in the BeThere group.

Facilitator fidelity to the intervention will be measured using a fidelity checklist. We will report the mean (SD) and median (IQR) scores on the fidelity checklist as an indicator of trial implementation quality.

Any major deviations from the protocol will be reported in the main outcomes paper.

20. Analysis populations

The primary analysis will be conducted on the intent-to-treat sample, meaning that all participants will be included and analyzed as randomized. No enrolled participants were excluded from the main analytic sample. We will also conduct a per protocol analysis including waitlist control participants who completed all assessments and did not participate in any BeThere intervention components and only BeThere intervention participants who completed seven or more intervention sessions and did not drop out of the study.

SECTION 5: TRIAL POPULATION

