- **Mechanisms of Action:** Total score on a 5-item measure developed to assess hypothesized mechanisms for the BeThere intervention (e.g., relaxation techniques, stress and anger management, positive parenting practices). Mechanisms of action were assessed at baseline, midline, endline, and follow up.
- **Caregiver psychological distress (see above)**
- **Caregiver stress (see above)**
- **Caregiver wellbeing (see above)**
- **Parenting (see above)**

Implementation variables

- **Attendance:** Number of sessions attended (participant-level; range: 0-9)
- **Facilitator competence:** ENACT score (12 of 15 items) measured post-training/pre-implementation and during training. We will operationalize facilitator competence as the % of harmful (item score=1) and % of not harmful (item score=3-4) behaviors observed
- **Intervention fidelity:** Total score on BeThere fidelity tool (8-items) assessing the number of intervention components adequately implemented per session (Range: 72-216)

Study outcome measures and timepoints

Measures	Baseline	Randomisation	Midline*	Endline	Follow up	Ongoing
Caregiver						
Parenting (BPS)	X			X	X	
Psychological Distress (K10)	X		X	X	X	
Caregiver stress	X		X	X	X	
Psychosocial wellbeing (WEMWBS)	X		X	X	X	
Child wellbeing (KINDL)	X			X	X	
Group cohesion (GCS)			X	X	X	
Mechanisms of action (MOA)	X		X	X	X	
Child						
Parenting (BPS – Child Version)	X			X	X	
Psychosocial wellbeing (KINDL)	X			X	X	
Randomisation		X				
Adverse events						X

*Midline assessments administered to BeThere study arm only

27a. Analysis methods

Data Management

We will prepare both a long and wide final dataset. The long dataset will include a separate observation for each assessment. The wide dataset will include one observation per individual with variables for each assessment period. The final dataset will include the following variables:

- Community identifier
- Household identifier
- Individual identifier (caregivers, child)
- Allocation [masked: will be coded 0 or 1 without a label until primary analyses are complete]
- BeThere group number/identifier
- Assessment number/time point
- Assessment date
- Caregiver age
- Child age
- Caregiver gender
- Number of caregivers in the household
- Caregiver-reported parenting items and total score
- Child-reported parenting items and total score
- Caregiver psychological distress items and total score
- Caregiver stress items and total score
- Caregiver wellbeing items and total score

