- Caregiver-reported child psychosocial wellbeing items and total score
- Child-reported psychosocial wellbeing items and total score
- Group cohesion items and total score
- Mechanisms of action items and total score
- Fidelity
- Number of sessions attended (in BeThere Group only)
- Facilitator competence

More details about each variable and how it will be operationalized is described in the appendix.

We will review the data and perform the following quality checks prior to beginning the analysis: 1) identify and input (if possible) any missing data using imputation; 2) review the distribution of all variables to identify any outliers or potential data entry errors, including reviewing the distribution of outcomes at each time point; and 3) search for any data irregularities. Any identified issues will be reviewed and reconciled with the research team. Once the dataset has been cleaned, we will proceed with creating and coding the variables required to answer the primary and secondary objectives. The variables used in the final analysis are described in the table below.

Descriptive statistics

The distribution of baseline characteristics will be reported for the overall sample and stratified by study arm. For each primary and secondary outcome, a summary of results will be presented by trial arm for each time point. We will summarize trial implementation indicators (BeThere attendance, facilitator competence, intervention fidelity) using descriptive statistics. Appropriate summary statistics will be applied to describe demographic, parenting, wellbeing, and implementation measures: mean and standard deviation for all symmetric (non-skewed) distributed measures; median, 25th and 75th quartiles for

skewed distributions. QQ plots and histograms will be used to assess data distributions of continuous measures. Categorical outcomes will be described using both numbers and proportions (percentage).

Loss to follow-up, active withdrawals from the trial, active withdrawals from treatment only, departures from randomised treatment and the prevalence of serious adverse events will be reported at follow-up.

Primary Analysis

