Appendix 1. Table Shells

1. Study variables (Section 25a)

Variable name	Variable description	Variable type	Variable coding/values
id	Unique ID. Each participant possesses a unique ID that indicates the community (1 st digit), family code (2 nd -4 th digit), and the participant type (5 th digit: female caregiver '1', male caregiver '2', or child '3').	Nominal	11111-99999
int_location	Community (numeric identifier) of residence	Nominal	1: Tbek 2: Ghoi 3: Sukzero/Taragok 4: Malou/Anglican Church/Lenguet 5: Pariak
household	Household (numeric identifier).	Nominal	1-9999
id_fv	Caregiver ID (numeric identifier)	Nominal	1-9999
Id_ch	Child ID (numeric identifier)	Nominal	1-9999
allocation	Study condition (BeThere vs. waitlist) Note: the labelling will not be revealed until after primary analyses have been completed	Nominal	0: TBC 1: TBC
betheregrp	BeThere group number Note: if waitlist groups are not enumerated then do not include this variable in the dataset until primary analyses have been completed	Nominal	1-99
assessment	Assessment number Note: do not include midline data until the primary analyses have been completed	Ordinal	0: Baseline 1: Midline 2: Endline 3: Follow up
assessweeks	Number of weeks since enrolment	Continuous	Time since baseline (in weeks)
assessdate	Date of the assessment	Date	DD-Mon-YY
cg_gender	Gender (caregiver)	Nominal	1: Female 2: Male
num_caregivers	Number of caregivers in the household	Continuous	1-2
ic_age_t1	Child age (in years; caregiver-reported)	Continuous	3-14
parenting	Total score on parenting measure (caregiver reported)	Numeric, continuous	24-120
parenting_01, parenting_02, parenting_03, parenting_04, parenting_05 (reverse), parenting_06, parenting_07,	Item score on parenting measure (caregiver-reported)	Numeric, continuous	1-5

parenting_08, parenting_09, parenting_10, parenting_11, parenting_12, parenting_13, parenting_14, parenting_15 (reverse), parenting_16, parenting_17 (reverse), parenting_18 (reverse), parenting_19 (reverse), parenting_20 (reverse), parenting_21, parenting_22, parenting_23, parenting_24			
parenting_warmth_cg	Total score on parenting warmth subscale (caregiver reported)	Numeric, continuous	17-85

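### Session attendance, recorded for the BeThere arm only, is listed in the same dataset as the masked allocation code and carries no instruction to withhold it

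*SAP*

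**What the plan says.** The masking commitment appears in several places. The Introduction (Section 2) states: "Analyst and PI will remain masked to study condition until primary analyses have been completed". Item 14 (Timing of final analysis) is more specific: "The statistician and PI will be masked to study condition during data collection, cleaning, and the primary effectiveness analyses". The mechanism is in the item 27a dataset list, under Data Management: "Allocation [masked: will be coded 0 or 1 without a label until primary analyses are complete".

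The same list goes on to name "Number of sessions attended (in BeThere Group only"), together with "Group cohesion items and total score", fidelity and facilitator competence.

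Appendix 1, table 1 (Study variables) attaches a masking instruction to three rows:

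- **allocation:** the labels are not revealed until the primary analyses are complete.
- **betheregrp:** left out of the dataset until then, if the waitlist groups are not numbered.
- **assessment:** "do not include midline data until the primary analyses have been completed".

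The rows for attendance, gcs, competence and fidelity have no such instruction.

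Item 27a also sets out quality checks to be done before analysis begins: dealing with missing data, including by imputation; reviewing the distributions of all variables for outliers and entry errors; and searching for irregularities.

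**The concern.** An unlabelled code masks the analyst only if nothing else in the file tells the two groups apart. A variable recorded in one arm alone does exactly that. The SAP's own label says that attendance is such a variable, and the plan sends the analyst to inspect it before the primary model is fitted.

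Participants and field workers know the allocation, and the primary outcome is reported by caregivers. Masking the analyst does nothing about reporting bias. It does protect decisions made on the data after collection, and the paper would presumably report it as a feature of the trial. If the code can be read at cleaning, decisions on outliers and imputation could be taken with knowledge of the arm, and the reported masking would not be what was delivered.

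**Working it through.** No figure is at stake, so the check sets the provisions side by side.

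**Step 1. When must masking hold?** Item 14 covers data collection, cleaning and the primary effectiveness analyses. The quality checks in item 27a are cleaning, so they fall inside this period.

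**Step 2. Does the dataset list apply during that period?** The list describes allocation as masked until the primary analyses are complete, so it describes at least in part the file as it stands while masking is in force. Appendix 1 supports this: it marks exceptions for items that must not be in the dataset yet.

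**Step 3. Which listed variables could identify the arm, and is each held back?**

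| Variable | Limited to BeThere? | Held back in Appendix 1? |
|---|---|---|
| betheregrp | Yes, if waitlist groups are not numbered | Yes, on that condition |
| Midline data | Yes (footnote to the timepoint table, item 26) | Yes |
| attendance | Yes, by its own label in item 27a | No |
| gcs, endline and follow-up | Not stated; the footnote limits midline only | No |
| fidelity | Measures BeThere delivery; not defined at participant level | No |
| competence | Measures facilitators; not defined at participant level | No |

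**Step 4. What would attendance show?** It is a participant-level count from 0 to 9 (item 26). If waitlist rows are blank, non-missing values occur under one allocation code only. If waitlist rows are filled with zeros, non-zero values occur under one code only. Either way, one cross-tabulation with allocation identifies BeThere. This does not depend on the arm sizes, which the SAP does not give.

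**Step 5. Do the general safeguards cover attendance?**

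- Item 14 postpones the secondary mediator analyses tied to intervention group characteristics, and those needing midline data, in order to preserve masking. That fixes when analyses are run. It does not say what the file contains, and it does not mention attendance.
- Item 9 (Trial design) lets blinding end when it becomes impossible within the primary analysis. The exposure here comes earlier, at cleaning, where item 14 promises masking.

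**Step 6. Is attendance needed before unmasking?** It is not in the primary model. It is needed for the per-protocol analysis, which under item 20 (Analysis populations) applies a session threshold to BeThere participants and a different rule to waitlist participants. That analysis cannot be run without knowing which code is which, and the SAP does not say that it follows the primary analyses.

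**The case against.** The strongest reply is that item 27a describes the final dataset, not the file released to the masked analyst. The list also contains the BeThere group number and the assessment time point, and Appendix 1 holds back the first conditionally and the midline data for the second. On that reading the masked release is a subset, and a data manager may well leave attendance out. This stands as far as it goes: the SAP describes no delivery step, so a reader might infer that masking fails the moment the file is opened, and the document does not show that. But the subset is defined only by the appendix notes, and attendance has none.

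A second reply concerns the other variables. A reader might infer that group cohesion, fidelity and competence also exist only in the BeThere arm. The document does not support this as a general statement.

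- **Group cohesion:** the secondary objective, "To assess the effect of group cohesion among beneficiaries in the BeThere intervention group on caregiver wellbeing and distress", points to one arm. However, the footnote restricts only the midline assessment, and the structural equation model for the effect of BeThere through cohesion would need values in both arms.
- **Fidelity:** this is a "Total score on BeThere fidelity tool (8-items) assessing the number of intervention components adequately implemented per session". Its range of 72 to 216 fits eight items over nine sessions scored 1 to 3 (8 × 9 × 1 = 72; 8 × 9 × 3 = 216), which is a delivery total and not a caregiver measure. The item scoring is inferred from the range.
- **Competence:** this is a facilitator rating.

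Fidelity and competence reveal the code only if they are merged onto caregiver rows. This reply stands in full, and these three variables can be raised only conditionally.

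A third reply is that little is left to discretion. The primary outcome, its time point and the model are set in item 27a, the reverse-scored items are set in Appendix 1, and item 28 (Missing data) limits prorating to 20% missing items. This too largely stands. What remains exposed is mainly the handling of outliers and the imputation decisions, for which item 27a gives no detailed rules.

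**Conclusion.** The point holds for attendance. Followed as written, the plan does not secure the masking that it promises during cleaning, because a variable that it labels as belonging to one arm is listed beside the unlabelled code, is not held back, and falls under a review of all variables before analysis.

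This rests on two assumptions: that the file used for cleaning matches item 27a apart from the appendix exceptions, and that attendance is blank or zero for waitlist participants, as its label implies. If the data manager already withholds attendance, only the wording needs correcting.

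The consequence is limited. The primary estimate is not invalidated, and the exposed decisions are mainly those on outliers and imputation. Nor does it follow that the SAP lacks a masking plan: the two withholding notes and the sequencing in item 14 show that the risk was recognised, and one clear route was left open. The correction is worth making because it is cheap and restores a protection that the SAP states explicitly.

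**What to change.** 1. Add to the attendance row in Appendix 1 the same kind of note as for midline data: not in the dataset until the primary analyses have been completed.
2. Add that note to fidelity and competence if they are linked to participant rows, and to endline and follow-up group cohesion if it was collected in BeThere only. State in the SAP which arms completed the cohesion scale at each time point.
3. Supply the withheld variables in a second file after the primary effectiveness analyses are locked.
4. Limit the masked quality check in item 27a to the variables released at that stage, and check the remainder when the second file arrives.
5. State in items 14 and 20 that the per-protocol analysis is run after that lock.

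If a file containing attendance has already gone to the statistician or PI, the report should say so and should say which cleaning decisions were still open at that time.

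The cost is a few lines of SAP wording and a two-step data release. No new data are needed, and the primary model does not change.

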21. Screening data

There were no diagnostic or clinical screening criteria for admission into the study.

22. Eligibility

The study aimed to enroll 960 caregivers and 400 children in Bor Country, South Sudan. Families were randomized to the BeThere intervention or waitlist control with 1:1 allocation and it is possible that more than one caregiver per family participated in the intervention. Randomization at the family-level ensured that caregivers from the same family were allocated to the same study arm. Individuals were eligible for the trial if they were:

- 1) Primary caregivers of children aged 3-14 years;
- 2) fluent in Dinka;
- 3) Living in Pariak, Ghoi, Taragok, Tibek, or Lenguet communities in Bor Country, Jonglei State, South Sudan; and 4) Willing to participate and commit to all nine sessions of BeThere.

For households with more than one caregiver, all caregivers must be willing to participate in order to be included. Individuals were excluded if they were less than 18 years of age, had participated in either a parenting or stress management intervention within the last six months, did not have a child aged 3-14 years, were unable to complete the assessment, were not fluent in Dinka, or were unwilling to give informed consent. One index child per household was randomly selected. If the selected index child was 7-14 years of age, they were also enrolled in the study and completed child-reported assessments at baseline, endline, and follow-up. If the index child was between 3-6 years of age, they did not complete an assessment. However, their caregivers were still enrolled and participated in study assessments. Not all households had more than one caregiver and/or an index child between the age of 7-14 years who agreed to participate.

[figure not shown]
23. Recruitment

Participants were recruited through community-based organizations, chiefs, and existing networks with whom War Child had established relationships. Recruitment methods included flyers, awareness sessions, door-to-door outreach, and word of mouth, and continued until the target of 192 participants per location was reached. Strategies used successfully in the pilot RCT were applied to engage male caregivers, such as scheduling around income-generating activities and tailoring messaging to their interests.

24. Withdrawal and loss to follow-up

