The analyses outlined in this strategy will be pragmatic, based on ITT and will utilize all available follow-up data from all randomised participants. The trial statistician will be blinded to treatment allocation. The main statistical analyses will establish the effectiveness of BeThere over waitlist control by comparing the mean difference of total parenting score at endline post randomization (see appendix).

Primary outcome

The primary outcome is the total score of the parenting scale at endline. We will compare randomized groups at endline and follow-up adjusted for baseline total score of parenting scale and account for hierarchical clustering of caregivers at the level of household. Specifically, we will fit a three-level random intercept linear regression model considering observations from endline and follow up at level 1, household at level 2 and community at level 3. The model will include the total score parenting scale at endline and follow up as the outcome variables with treatment group, baseline rate of parenting total score as explanatory variables. A time by treatment interaction will be included to allow the effect to differ at each time point (endline, follow up).

Secondary outcomes

Secondary outcomes as listed will be assessed with a similar methodology for the primary outcomes, using generalized linear mixed models with the appropriate link function/distribution. Normal outcomes will use an identity link function, binary variables would use a logit link function, and Poisson (count) variables would use a log link function. We will use all available time points in the model and extract differences at endline and follow up post-randomisation. All the questionnaires to be used have validated methods of scoring.

Method for handling non-compliance

In addition to the primary intention-to-treat analysis the effect of actually receiving treatment as defined in the protocol will also be estimated using a per-protocol analysis (PP). The PP analysis will remove data of those who:
attended fewer than seven sessions and any participant who did not complete all study assessments.

Planned sensitivity analysis

As a sensitivity analysis, we will replicate the effectiveness models excluding Community #1: Tibek due to implementation issues and delays. We will conduct subgroup analyses for the effectiveness models

stratified by gender of the caregiver, number of caregivers in the household (1 vs. 2), and child age (3-7 years vs. 8-14 years).

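### The primary model has no caregiver level, so in two-caregiver households the endline standard error is modestly too large and the time-by-treatment standard error more so

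*SAP*

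**What the plan says.** Section 27a (Primary outcome) says the analysis will "account for hierarchical clustering of caregivers at the level of household". It then names the levels: "considering observations from endline and follow up at level 1, household at level 2 and community at level 3". Both post-baseline scores enter the same model: "The model will include the total score parenting scale at endline and follow up as the outcome variables". A treatment-by-time interaction gives an effect at each visit. No caregiver random effect and no within-caregiver residual correlation is named there or elsewhere.

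Section 22 states that "it is possible that more than one caregiver per family participated in the intervention", and on allocation: "Randomization at the family-level ensured that caregivers from the same family were allocated to the same study arm". The planned subgroup analyses split households into those with one and those with two caregivers, and Appendix 1 codes the number of caregivers as 1 or 2. The planned dataset in Section 27a holds both a household and an individual identifier. Secondary outcomes are to follow the approach of the primary outcome.

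**The concern.** The data are nested as visit within caregiver within household within community. The written model goes straight from visit to household. A two-caregiver household supplies four scores, and a household intercept alone forces one common covariance on all six pairs of them. Two of those pairs are the same person at two visits; the other four are two different people. If a person resembles themselves more than they resemble the other caregiver, the fitted covariance is a compromise that is wrong for both kinds of pair.

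At stake are the standard error and confidence interval of the primary endline effect, those of the interaction, and the same quantities for every caregiver-reported secondary outcome. In a one-caregiver household the household intercept already acts as the caregiver intercept. Child-reported outcomes come from one index child per household. Neither is affected.

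**Working it through.** The SAP states no intraclass correlation, standard error or design effect for this model, so there is no figure of its own to reproduce on this point.

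**Inputs from the SAP.** Model levels and two post-baseline scores per caregiver (Section 27a); one or two caregivers per household (Sections 22 and 27a, Appendix 1); allocation by family (Section 22); 956 caregivers enrolled (Section 11), hence at most 956/2 = 478 two-caregiver households.

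**Assumptions.** Total variance 1 at each visit; correlation *w* between two visits of one caregiver; correlation *b* between two caregivers of one household, the same within and across visits; complete data. Community and baseline terms are left out, so read *w* and *b* as the correlations remaining after baseline adjustment.

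**Closed form, every household with two caregivers.**

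- Common correlation fitted by the written model: r = (2w + 4b)/6 = (w + 2b)/3.
- Endline, variance of a household mean: model (1 + r)/2, true (1 + b)/2.
- Follow-up minus endline, variance of a household mean change: model 1 − r, true (1 + b) − (w + b) = 1 − w.
- Time average: model (1 + 3r)/4, true (1 + w + 2b)/4. These are equal because 3r = w + 2b.

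**Example, w = 0.6 and b = 0.2.**

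- r = (0.6 + 0.4)/3 = 0.333, so the residual variance is 0.667 against a true 0.40.
- Endline: √(1.333/1.2) = 1.054. With 239 households per arm, the reported standard error is √(2 × 0.667/239) = 0.0747 SD and the true one √(2 × 0.6/239) = 0.0709 SD.
- Interaction: √(0.667/0.4) = 1.29.
- Time average: 0.5 against 0.5, ratio 1.00.

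**Mixed household sizes.** Here the household-only model was fitted to the assumed covariance by maximum likelihood, and its reported standard error was divided by the true (sandwich) one. The actual two-sided type I error is 2[1 − Φ(1.96 × ratio)].

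| Two-caregiver / one-caregiver households | w | b | Endline ratio (type I) | Interaction ratio (type I) |
|---|---|---|---|---|
| 478 / 0 | 0.6 | 0.05 | 1.084 (0.034) | 1.384 (0.0067) |
| 478 / 0 | 0.8 | 0.2 | 1.080 (0.034) | 1.732 (0.0007) |
| 478 / 0 | 0.6 | 0.2 | 1.054 (0.039) | 1.291 (0.011) |
| 278 / 400 | 0.6 | 0.2 | 1.040 (0.041) | 1.209 (0.018) |
| 78 / 800 | 0.6 | 0.2 | 1.015 (0.047) | 1.075 (0.035) |
| 78 / 800 | 0.4 | 0.3 | 1.004 (0.049) | 1.013 (0.047) |

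The table holds the extremes of six pairs tried (w/b = 0.4/0.1, 0.4/0.3, 0.6/0.05, 0.6/0.2, 0.6/0.4, 0.8/0.2). They do not fill the whole rectangle. The untried corner 0.8/0.05 with all households paired gives r = 0.3, hence √(1.3/1.05) = 1.11 at endline and √(0.7/0.2) = 1.87 for the interaction. The ratio is 1.00 if w = b, if no household has two caregivers, or once a caregiver intercept is added.

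**Power.** Assuming 80% nominal power (an illustrative value), the power is Φ(2.80 − 1.96 × ratio). A ratio of 1.05 gives Φ(0.74), about 77%. A ratio of 1.084 gives Φ(0.68), about 75%.

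**The case against.** The strongest reply is that the model keeps a random intercept at the unit of randomisation. The usual failure, treating members of one household as independent, therefore does not occur. The primary contrast is at endline, where the error is at most about 8% in the scenarios tabulated and runs in the safe direction. The larger error falls on the interaction, which the SAP includes to obtain visit-specific effects and does not set up as a hypothesis of its own. Not every household has two caregivers, and this shrinks the error further. All of this stands, and it limits the weight of the point. It does not remove it: the levels are listed explicitly, caregiver is not among them, and nothing elsewhere supplies the missing correlation.

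A reader might infer that the missing level can also make standard errors too small. The documents do not support that. Take w = 0.4, with 0.4 between caregivers at the same visit and 0.2 across visits. The written model does give ratios below 1: r = (0.4 + 0.4 + 0.2)/3 = 0.333, endline √(1.333/1.4) = 0.976, interaction √(0.667/0.8) = 0.913. But adding the caregiver intercept lowers them: its between-caregiver covariance is (0.4 + 0.2)/2 = 0.3, giving √(1.3/1.4) = 0.964 and √(0.6/0.8) = 0.866. The cause there is an absent household-by-visit term, which is a separate matter.

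A reader might also fault the random community level or the unlisted time main effect. Allocation was balanced within each community, and an interaction of this kind is ordinarily fitted with its main effects. Those are points of preference and wording, and nothing here rests on them.

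**Conclusion.** The point holds as a modest, conservative misspecification of the primary model. Over the six correlation pairs and 78 to 478 two-caregiver households, the reported standard error is about 0 to 8% too large for the endline effect and about 1 to 73% too large for the time-by-treatment term. It is correct for the time-averaged effect. The cost is precision: intervals that are too wide and, at ratios of 1.05 to 1.08, a nominal 80% power that falls to about 75 to 77%. No false positives arise in these scenarios.

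The size rests on correlations and a household mix that the SAP does not give, and missing visits were not modelled. That the caregiver level is absent rests on the SAP's text alone. The change is worth making because it is cheap and makes the model match the SAP's own statement about clustering of caregivers.

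**What to change.** In Section 27a, state the levels as observation, caregiver, household and community, with a random intercept for caregiver within household. Apply this to the primary outcome and to all caregiver-reported secondary outcomes. Child-reported outcomes need no caregiver level.

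Where two caregivers' scores may agree more at the same visit than across visits, also add a household-by-visit random term. The clearest case is caregiver-reported child wellbeing, where both caregivers may rate the same index child. The caregiver intercept alone does not correct for that.

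The cost is one or two extra variance components, which may be poorly estimated if few households have two caregivers. The identifiers are already in the planned dataset and no new data are needed. If allocation is still masked under Section 14, the change can be made without knowledge of the results by arm.
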